11.2.5. Body weight and body mass index

Body mass index (BMI) will be calculated as body weight (kg) /[height (meters)]2.

Changes in body weight and BMI at each post-baseline time point will be calculated as the post-baseline value minus the baseline value (Visit 2).

11.2.6. Magnetic resonance imaging

Individual patient data will be assessed for treatment-emergent ARIA.

11.3. Calculation or derivation of pharmacokinetic variables

A population PK analysis of plasma AZD3293 and AZ13569724 concentration data will be performed. The population PK analysis will involve standard PK structural modelling techniques using nonlinear mixed effects modelling to obtain population mean and variance values of specific PK parameters for AZD3293 and AZ13569724. Potential covariate effects will be investigated as predictors of variability in AZD3293 and AZ13569724 PK. Plasma AZD3293 and AZ13569724 concentration-time data from previous AZD3293 clinical pharmacology studies may be combined with data from this study. The results of the population PK analysis will be provided in a separate report.

11.4. Calculation or derivation of pharmacodynamic variable(s)

11.4.1. Cerebrospinal fluid biomarkers

Changes from screening in CSF biomarker concentrations of $A\beta_{1-40}$, $A\beta_{1-42}$, total tau, phosphorylated tau and other, exploratory biomarkers (eg, sAPP β) will be calculated for each post-baseline time point.

Changes in biomarker concentration will be calculated as the post-baseline value minus the predose value.

11.4.2. Imaging biomarkers

Volumetric MRI and PET imaging variables will be derived by the respective central imaging vendors and provided in agreed database format.

Changes from screening/baseline will be calculated as the post-baseline value minus the predose value.

11.4.3. Relationship between pharmacokinetic and pharmacodynamic variables

Plasma and CSF AZD3293 concentrations in relation to PD (biomarkers and cognitive markers) and other measures as appropriate will be examined graphically using plots showing predicted exposure to AZD3293 (AUC) and PD measures/markers.

11.4.4. Population analysis of pharmacokinetic/pharmacodynamic variables

A population PK/PD analysis implementing appropriate structural models will be conducted following completion of the study to examine the relationships between AZD3293 and/or AZ13569724 and selected measures of efficacy (eg, the primary efficacy endpoint) or tolerability (eg, AE incidence) using nonlinear mixed effects modelling. The results of the population PK/PD analysis will be provided in a separate report.

11.5. Calculation or derivation of pharmacogenetic variables

Pharmacogenetic outcomes for mRNA and miRNA in selected species will be calculated as change from baseline quantified with reverse transcription polymerase chain reaction (RT-PCR) or equivalent technology. Genetic variation in baseline DNA will be measured by direct resequencing of selected genes, including intronic and promoter regions. Techniques may be modified as scientific advances are made.

11.6. Calculation or derivation of health economic variables

Changes in RUD-Lite and EQ-5D-5L scores at each post-baseline timepoint will be calculated as the post-baseline value minus the baseline value (Visit 2).

12. STATISTICAL METHODS AND SAMPLE SIZE DETERMINATION

12.1. Description of analysis sets

12.1.1. Efficacy

The Full Analysis Set will group patients according to randomized treatment assignment, even if the patient does not take the assigned treatment, does not receive the correct treatment, switches to a different treatment group if the assigned treatment group is dropped at an interim analysis, or otherwise does not follow the protocol. When change from baseline is assessed, patients will be included in the analysis only if both a baseline and at least 1 valid post-baseline measure are available.

For the longitudinal CSF biomarker and PET (amyloid) sub-studies, the analysis sets will include all those patients whose eligibility was determined by the respective biomarker, who signed consent for the respective sub-studies, and who have a baseline and at least 1 valid post-baseline CSF assessment or PET scan.

12.1.2. Safety

All patients who received at least 1 dose of randomized study treatment (AZD3293 or placebo) will be included in the safety analysis set. In safety data presentations, erroneously treated patients (eg, those randomized to "Treatment A" but actually given "Treatment B") will be accounted for in their actual treatment groups. If an AZD3293 dose group is dropped following an interim analysis (see Section 12.2.2), patients switched to the remaining AZD3293 dose and remaining on treatment will be accounted for as a separate group.

12.1.3. Pharmacokinetics

The PK analysis set is defined as all patients in the safety population who have at least 1 post-dose PK assessment. The population PK analyses will be performed using this analysis set.

12.2. Methods of statistical analyses

12.2.1. General principles

The aim of the primary analysis is to evaluate whether at least 1 dose of AZD3293 is superior to placebo in slowing disease progression in patients with early AD (ie, the continuum of patients with MCI due to AD and patients diagnosed with mild dementia of the Alzheimer's type), as measured by change from baseline in ADAS-Cog₁₃ total score at Week 104.

The aim of the secondary analyses are to evaluate whether AZD3293 is superior to placebo for other outcomes as measured by the secondary endpoints: FAQ score, ADCS-ADL score, CDR-SB score, iADRS, MMSE, time in the current disease state (CDR global score), NPI total score, to evaluate the clinical worsening and need for symptomatic treatments, and biomarkers that may be indicative of disease modification.

A comprehensive Statistical Analysis Plan (SAP; including biomarker analyses), as well as separate population PK and PK/PD analysis plans, will be prepared and finalized before the study data are unblinded. An interim analysis SAP will be prepared and finalized before each interim analysis.

12.2.2. Interim analyses

Four interim analyses may be conducted during this study. The IDMC charter will specify the final details of the interim analyses. Every effort will be made to implement this study in such a way that only IDMC members (see Section 12.4) and a ring-fenced external Independent Statistical Center will have access to unblinded data emerging from the study. Furthermore, every effort will be made to conceal any of the predefined design adaptations during the course of the study to any party involved in the conduct of the study. Maintaining validity and integrity of the study is of paramount importance to ensure its acceptability to the sponsor, the scientific community, and health authorities. The sponsor Executive Committee will be established to review the IDMC recommendations in accordance with the prespecified objectives of the interim analyses. Sponsor staff with direct roles in study conduct will not have access to the results of the interim data analyses.

12.2.2.1. Interim analysis 1

The first interim analysis (IA1) will be performed when approximately 70 patients per group have 13 weeks' worth of data. It is expected that, at IA1, approximately 500 patients will have been randomized globally. The objective of IA1 is to assess the viability of continuing with AZD3293 with regard to safety.

One of the following IDMC recommendations will result from IA1:

- Continue the study unmodified
- Discontinue enrollment in 1 or both AZD3293 treatment groups for reasons of an unacceptable safety profile.
 - If 1 AZD3293 treatment group is discontinued for enrollment at IA1, the randomization ratio for newly enrolled patients will remain 2:1 (active:placebo).
 Patients in the discontinued AZD3293 treatment group will be switched to the other AZD3293 treatment group; for analysis purposes, these patients will be included in their originally assigned AZD3293 treatment group.
 - Stop the study if enrollment in both AZD3293 treatment groups is discontinued

12.2.2.2. Interim analysis **2**

The second interim analysis (IA2) will be performed when approximately 80% of patients have been randomized. IA2 will assess the viability of continuing AZD3293 treatment groups with regard to safety and will re-assess the total sample size based on the Bayesian posterior predictive probabilities of the ADAS-Cog₁₃, ADCS-iADL, and/or FAQ. Further details will be described in the interim analysis SAP and finalized prior to unblinding of efficacy data.

Any necessary sample-size adjustment will be recommended to the sponsor Executive Committee

One or more of the following IDMC recommendations will result from IA2:

- Continue the study unmodified
- If neither AZD3293 treatment group was discontinued at IA1 and, therefore, both AZD3293 treatment groups remain in the study at IA2:
 - Discontinue enrollment in 1 or both AZD3293 treatment groups for reasons of an unacceptable safety profile. If 1 dose is discontinued for enrollment at IA2, the randomization ratio for newly enrolled patients will remain 2:1 (active:placebo). Patients in the discontinued AZD3293 treatment group will be switched to the other AZD3293 treatment group; for analysis purposes, these patients will be included in their originally assigned AZD3293 treatment group.
 - Stop the study if both AZD3293 treatment groups are discontinued
- If 1 AZD3293 treatment group was discontinued at IA1 and, therefore, 1 AZD3293 treatment group remains in the study at IA2:
 - Discontinue enrollment in the remaining AZD3293 treatment group for reasons of an unacceptable safety profile
 - Stop the study if the remaining AZD3293 treatment group is discontinued
- Increase the sample size

12.2.2.3. Interim analysis 3

A maximum of 2 additional interim analyses may occur following IA2. A futility interim analysis (IA3) may be performed if the study sample size does not increase at IA2 or there is decreased confidence in current clinical trial design based on external data.

12.2.2.4. Interim analysis 4

An additional interim analysis (IA4) may be performed to assess for futility and for early stopping of the study for efficacy. Data cut-off for IA4 would occur approximately 52 weeks after the last patient is randomized; however, it may occur later or earlier than this expected date if external data warrant.

To control for the remote possibility that the study will be stopped for efficacy, a Haybittle-Peto adjustment (Haybittle 1971, Peto et al 1976) will be used if efficacy is tested at IA4. A significance level of α =0.001, will be used for treatment comparisons at the start of the multiplicity graph. The final analysis will use a significance level of α =0.05 for treatment comparisons between the AZD3293 treatment groups and the placebo group at the start of the multiplicity graph (see Section 12.2.3). Further details will be described in the interim analysis SAP.

12.2.3. Multiplicity adjustments

The proposed study design contains several elements that require multiplicity adjustments to strongly control the family-wise error rate (FWER):

- Comparison of 2 AZD3293 treatment groups with the placebo group
- Changing the randomization ratio to 2:1 if a dose is dropped at the first or second interim analysis
- Sample size re-estimation at the second interim analysis

The first element, comparisons of the 2 AZD3293 treatment groups with the placebo group, is addressed by the use of a multiplicity graph. A graphical multiplicity strategy will be used for testing key secondary hypotheses to protect against Type I error of falsely rejecting a null hypothesis. The use of a prespecified analysis plan that employs Bretz' graphical approach will provide strong control of the study-wise Type I error rate for the primary and key secondary hypotheses at level α =0.05 (Bretz et al. 2009, 2011). The specific multiplicity graph will be detailed in the SAP.

In addition, to strongly control the FWER, a confirmatory adaptive design should satisfy the conditional invariance principle (Brannath et al 2007): separate test statistics will be calculated from the 2 patient cohorts (those patients enrolled prior to the second interim analysis [IA2], and those enrolled after IA2) and combined in a prespecified way (using the weighted inverse normal p-value combination method) for the final test decisions. Hence, any design modification that preserves the distributional properties of the separate test statistics under a given null hypothesis of interest will not lead to an inflation of the FWER. The p-value combination test principle combines the 2 p-values using a prespecified combination function and by construction satisfies the invariance principle. Details on the implementation of the measures to strongly control the FWER will be provided in the statistical analysis plan

A separate family of biomarkers will be tested at α =0.05. The family will include the biochemical biomarkers (CSF A β 1-42, total tau, and phosphorylated tau), as well as imaging biomarkers (amyloid PET and volumetric MRI).

12.2.4. Efficacy

All analyses will be performed in a manner that is consistent with the intent-to-treat (ITT) principle. An ITT analysis is an analysis of data by the groups to which patients are assigned by random allocation, even if a patient does not take the assigned treatment or does not receive the correct treatment, or otherwise does not follow the protocol or is not followed to the end of the study (ie, Week 104). If a treatment group is dropped at an interim analysis, the data from those patients will be analyzed according to the treatment group to which the patients were originally randomized. When change from baseline is assessed, a modified ITT (mITT) approach will be used; patients will be included in the analysis only if both a baseline and a post-baseline measure are available.

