One or more of the following IDMC recommendations will result from IA2:

- Continue the study unmodified
- If neither AZD3293 treatment group was discontinued at IA1 and, therefore, both AZD3293 treatment groups remain in the study at IA2:
 - Discontinue enrollment in 1 or both AZD3293 treatment groups for reasons of an unacceptable safety profile. If 1 dose is discontinued for enrollment at IA2, the randomization ratio for newly enrolled patients will remain 2:1 (active:placebo). Patients in the discontinued AZD3293 treatment group will be switched to the other AZD3293 treatment group; for analysis purposes, these patients will be included in their originally assigned AZD3293 treatment group.
 - Stop the study if both AZD3293 treatment groups are discontinued
- If 1 AZD3293 treatment group was discontinued at IA1 and, therefore, 1 AZD3293 treatment group remains in the study at IA2:
 - Discontinue enrollment in the remaining AZD3293 treatment group for reasons of an unacceptable safety profile
 - Stop the study if the remaining AZD3293 treatment group is discontinued

• Increase the sample size

Interim analysis 3

A third interim analysis (IA3) may be performed to calculate the futility of either dose. The parameters of this futility analysis will be described in the interim analysis and the end-of-study analysis SAPs.

Interim analysis 4

A fourth interim analysis (IA4) may be performed to assess for futility and for early stopping of the study for efficacy. This interim analysis will be described in the interim analysis and end-of-study analysis SAPs.

Efficacy analyses

All analyses will be performed in a manner that is consistent with the intent-to-treat (ITT) principle. When change from baseline is assessed, patients will be included in the analysis only if both a baseline and a post-baseline measure are available.

Primary analysis

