3.2.4. Study Plan

The Study Plan is described in Table 2 below.

Table 2. Study Plan (D5010C00009)

Study procedure ^a	Screening	Period ^b	Double-blind treatment period															ED ^d	F/U			
Visit number	V1	V2 ^c	V3	V4	V5	V6	V7	V8	V9	V10	V11	V12	V13	V14	V15	V16	V17	V18	V19	V20		V21
Study week			1	4						39					$71^{\rm f}$			91	97	104		108-110 ^g
Tolerance interval for Visit			±3	±3						±7		±10	±7	±7	±7	±7	±7	±7	±7	±10		
(days)																						
Informed consent	X																					
Demographics	X																					
Medical /psychiatric History	X																					
Prior/concomitant treatments	X	X	X	X	X	X	X	X	X	X	X	X	X	X	X	X	X	X	X	X	X	X
Inclusion/exclusion criteria	X	X																				
NIA-AA criteria review	X										X								X		X	
FAQ		X						X				X				X				X	X	
ADCS-ADL		X						X				X				X				X	X	
CDR ^h	X							X				X				X				X	X	
MMSE	X					X		X				X				X				X	X	
RBANS	X										X								X		X	
ADAS-Cog ₁₃		X				X		X				X				X				X	X	
NPI		X						X				X				X				X	X	
Letter & Category Fluency, Digit		X						X				X				X				X	X	
Symbol-Coding tests																						
EQ-5D-5L (patient)		X					X				X					X				X	X	
RUD-Lite		X					X				X					X				X	X	
MRI ⁱ	X											X								X	X	
Florbetapir F 18 Amyloid PET	X																			X	X	
Lumbar puncture ^j	X											X							X		X	
Blood sample for plasma AZD3293 and AZ13569724 PK ^k				X^{l}			X ^m			X ^l	X ^l			X^{m}				X ⁿ			X	
Blood sample for plasma biomarkers ^o		X										X							X		X	

Study procedure ^a	Screening	Double-blind treatment period															ED ^d	F/U				
Visit number	V1	V2 ^c	V3	V4	V5	V6	V7	V8	V9	V10	V11	V12	V13	V14	V15	V16	V17	V18	V19	V20		V21
Study week			1	4	7	13	19	26	32 ^f	39	45	52	58 ^f	65	71 ^f	78	84 ^f	91	97	104		108-110 ^g
Tolerance interval for Visit			±3	±3	±7	±7	±7	±7	±7	±7	±7	±10	±7	±7	±7	±7	±7	±7	±7	±10		
(days)																						
Blood sample for APOE genotyping ^p	X																					
Blood sample for pharmacogenetics ^q	X																					
Blood samples for pharmacogenomics ^q		X										X							X		X	
Laboratory tests ^r	X	X		X	X	X		X		X		X		X		X		X		X	X	
Urine drug screen	X																					
Physical, neurological examinations	X	X		X ^s		X		X ^s		X ^s		X		X ^s		X ^s		X ^s		X	X	
Comprehensive eye examination ^t		X										X								X	X	
Skin examination ^u		X				X						X				X				X	X	
Vital signs ^v	X	X	X	X	X	X	X	X		X	X	X		X		X		X	X	X	X	X
Height	X																					
Body weight	X	X				X		X				X				X				X	X	

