12-Lead ECG	X	X^{w}	X	X		X		X		X		X		X		X			X	X	X	X
C-SSRS ¹		X	X	X		X	X	X		X	X	X		X		X		X	X	X	X	
Dispense drug		X	X	X	X	X	X	X		X	X	X		X		X		X	X			
Assess drug compliance ^x			X	X	X	X	X	X	X^{x}	X	X	X	X ^x	X	X ^x	X	X ^x	X	X	X	X	
Adverse events	X	X	X	X	X	X	X	X	X	X	X	X	X	X	X	X	X	X	X	X	X	X
Addenda (site specific)										•					•		•					
FDG PET or		X																		X	X	
¹⁸ F-AV-1451 PET		X										X								X	X	
US Medicare Claims ²		X																				

- a Every effort should be made for visits to occur on the designated study days. The overall treatment period in the protocol should be maintained (ie, visits should be scheduled based on the randomization date rather than the previous visit).
- The screening process will take place over more than 1 day. After consent is obtained, most screening procedures will be performed at a single visit, however additional screening visits will be necessary for some procedures, eg, MRI, lumbar puncture, etc. In addition, it may sometimes be necessary for patients to return for repeat assessments (eg, if MRI does not pass the quality control process). Therefore, the duration of the screening period may be increased with the permission of the column medical monitor and is not necessarily considered a screen failure. See Section 3.2.2 for order of MRI and LP testing and Section 6.3.4.1 for order of cognitive testing.
- First dose to be administered the day after Visit 2 (randomization), preferably in the morning.
- All patients who discontinue study treatment before Week 104 should have Early Discontinuation (ED) procedures and assessments performed as soon as possible. ADCS-ADL, FAQ, CDR, MMSE, RBANS, ADAS-Cog₁₃, NPI, and Letter & Category Fluency, Digit Symbol-Coding tests should be conducted at the early discontinuation visit if it has been more than 12 weeks since they were last administered. MRI, and for longitudinal sub-study participants, florbetapir F 18 amyloid PET and lumbar puncture, should only be performed if it has been at least 24 weeks since the previous assessment.

 Note: Patients should be encouraged to remain in the study after their ED Visit until Week 104 (Visit 20), even if study treatment has been discontinued. Patients who discontinue treatment, but remain in the study should continue to participate in all scheduled visits and assessments, as appropriate, with the exception of PK measurements and PET scans.
- Footnote e has been deleted

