12.2.4.1. Primary analysis

The primary efficacy endpoint, change from baseline at Week 104 in ADAS-Cog₁₃ total score, will be analyzed using an MMRM model that includes the fixed effects of treatment, visit (categorical covariate), treatment-by-visit interaction, disease status at baseline (MCI due to AD or mild AD), APOE4 status (carrier versus non-carrier), baseline ADAS-Cog₁₃ total score (continuous covariate), concomitant AChEI use at baseline (yes/no), age at baseline, country, and baseline ADAS-Cog₁₃ total score-by-visit interaction. An unstructured variance-covariance matrix will be used.

For each of the 2 AZD3293 treatment groups, the null hypothesis is that the change from baseline in ADAS-Cog₁₃ total score at Week 104 is equal to the change from baseline in ADASCog₁₃ total score at Week 104 for the placebo treatment group. The alternative hypothesis is that the change from baseline in ADAS-Cog₁₃ total score at Week 104 for an AZD3293 treatment group ($\mu_{AZD3293}$) is not equal to the change from baseline in ADAS-Cog₁₃ total score at Week 104 for the placebo treatment group ($\mu_{Placebo}$). These hypotheses can be represented as follows:

 H_{Null} : $\mu_{\text{AZD3293}} = \mu_{\text{Placebo}}$

 $H_{Alternative}$: $\mu_{AZD3293} \neq \mu_{Placebo}$

The primary analysis will evaluate whether there is a difference between treatment groups in the mean change from baseline in ADAS-Cog₁₃ total score at Week 104 and will be based on the treatment difference at Week 104 using least-squares means. This will be accomplished by using appropriate linear contrasts of the parameters in the model described above.

As a sensitivity analysis, a method for missing value imputation based on pattern mixture models will be implemented. It is assumed that after discontinuation from the study, patients receiving the AZD3293 doses will exhibit the same future evolution of the disease as patients on placebo treatment. This method uses sequential regression and multiple imputation methodology to impute missing values for visits after a patient's discontinuation from the study. Based on the available data from placebo-treated patients, the missing values from the placebo and AZD3293 treatment groups will be imputed sequentially using a procedure for monotone missing data patterns until all visits are imputed.

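### The mITT rule, as written, also governs the placebo-based imputation and so leaves the earliest study withdrawers out of the check on withdrawal (minor, cheap to improve)

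*Protocol*

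**What the plan says.** Three places in the Protocol restrict change-from-baseline analyses.

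- Synopsis, Efficacy analyses: "When change from baseline is assessed, patients will be included in the analysis only if both a baseline and a post-baseline measure are available".
- 12.1.1, Full Analysis Set: "patients will be included in the analysis only if both a baseline and at least 1 valid post-baseline measure are available".
- 12.2.4, which opens by speaking of all analyses and labels the restriction a modified ITT (mITT) approach: "patients will be included in the analysis only if both a baseline and a post-baseline measure are available".

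Section 12.2.4 also defines ITT as analysis by assigned group, including patients who are not followed to Week 104.

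Section 12.2.4.1 describes one sensitivity analysis of the primary endpoint, a placebo-based multiple imputation for visits after study discontinuation. Its premise is this: "It is assumed that after discontinuation from the study, patients receiving the AZD3293 doses will exhibit the same future evolution of the disease" as placebo patients. Missing values in all groups are "imputed sequentially using a procedure for monotone missing data patterns until all visits are imputed". The section names no separate patient set for this analysis.

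In Table 2 (3.2.4), ADAS-Cog13 is given at Visit 2 and next at Visit 6, Week 13 (±7 days). For patients who stop early, the table's note says that the scales, ADAS-Cog13 among them, "should be conducted at the early discontinuation visit if it has been more than 12 weeks since they were last administered".

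**The concern.** A patient who leaves the study within about 12 weeks of baseline has no scheduled post-baseline ADAS-Cog13. Under the stated rule that patient enters no change-from-baseline analysis.

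For the MMRM this costs essentially nothing, because a patient without post-baseline outcomes contributes no outcome data. The placebo-based imputation is different. A patient with only a baseline score can be imputed from placebo data and then counts in the arm mean with no drug effect. So a rule that is harmless in the primary model carries over to the one described analysis where it changes the estimate.

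The set is then selected on an event after randomization, and it omits the withdrawers with the least exposure. When the drug works, the omission moves the estimate in the drug's favour. At stake is how well one supportive analysis does its job, not the primary result.

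**Working it through.** **Inputs from the Protocol**

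- 734 patients per group, 2202 in total (12.3.1).
- 104-week differences (SD): mild AD 3.83 (13.54), MCI 2.24 (12.96) (12.3.1).
- Mix of 65% mild AD and 35% MCI (note to Table 7).
- Discontinuers assumed to have 50% of the completers' effect (12.3.1).
- 30% dropout over the study (12.3.2.3).

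**Reproducing the plan's figures**

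- Completers: 2202 × 0.70 = 1541.4 (stated 1541), or 513.8 per group (stated about 514).
- Power with 734 per group, effect size 0.21 and two-sided α = 0.025: 96.3% (stated 96%).
- Overall adjusted effect size at 30% dropout: (0.65 × 0.28 + 0.35 × 0.17) × (1 − 0.5 × 0.30) = 0.205 (stated 0.21).

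The last line is compatible with 30% but does not confirm it. With the unrounded ratios in 12.3.1, the adjusted MCI ADAS-Cog effect size implies 32-44% discontinuation and the mild AD iADL one implies 21-30%, and these ranges do not overlap. I rely only on the 30% stated in 12.3.2.3.

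**Step 1: share with no post-baseline score, e.** The protocol gives no dropout timing, so both patterns are assumptions.

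- Even spread: 0.30 × 12/104 = 3.46%, or 25 per arm and 76 of 2202.
- Constant hazard: 1 − 0.70^(12/104) = 4.03%, or 30 per arm and 89 of 2202.

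The 12-week cut is approximate. A patient who leaves with no early discontinuation visit can be missed up to Visit 6. Taking Week 14 instead gives 4.0-4.7% (30-34 per arm).

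**Step 2: planning difference and standard error**

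- Difference: 0.65 × 3.83 + 0.35 × 2.24 = 3.2735 points.
- SD: 0.65 × 13.54 + 0.35 × 12.96 = 13.34.
- SE: 13.34 × √(2/734) = 0.696, a simple approximation.

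**Step 3: effect of the rule.** Let B be the mean benefit with everyone included and early leavers contributing zero. Removing a share e whose contribution is zero gives B/(1 − e). The relative inflation is 1/(1 − e) − 1, which is 3.59% for even spread and 4.20% for constant hazard, whatever benefit later leavers keep. If B = 0, the shift is zero.

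**Step 4: in ADAS-Cog points**, for three assumptions about patients who leave after Week 12:

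- Fully placebo-like: B = 0.70 × 3.2735.
- Half the effect, as in 12.3.1: B = [0.70 + 0.5 × (0.30 − e)] × 3.2735.
- Keep the benefit accrued linearly to departure. Even spread: B = [0.70 + 0.2654 × 58/104] × 3.2735, where 0.2654 = 0.30 × 92/104 is the later-leaving share and 58 is its mean departure week. Constant hazard: the same integral gives 0.1388 in place of 0.1480.

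| Later leavers | Timing | All with baseline | mITT rule | Shift | In SE |
|---|---|---|---|---|---|
| Placebo-like | Even | 2.291 | 2.374 | +0.082 | 0.12 |
| Placebo-like | Constant hazard | 2.291 | 2.388 | +0.096 | 0.14 |
| Half effect | Even | 2.726 | 2.824 | +0.098 | 0.14 |
| Half effect | Constant hazard | 2.717 | 2.831 | +0.114 | 0.16 |
| Accrued benefit kept | Even | 2.776 | 2.875 | +0.100 | 0.14 |
| Accrued benefit kept | Constant hazard | 2.746 | 2.861 | +0.115 | 0.17 |

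On the half-effect assumption, power in this analysis is 95.3-95.4% under the rule and 94.5-94.6% with everyone included, a change of less than 1 percentage point.

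**Step 5: a less favourable timing.** If dropout were front-loaded so that 6-8% left by Week 12 (44-59 per arm, an assumption with no source in the protocol), the inflation would be 6.4-8.7%. At 8%, on the half-effect assumption, the estimates are 2.882 and 2.652, a shift of 0.23 point or 0.33 SE.

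**The case against.** **The specific text governs the general rule.** Section 12.2.4.1 describes imputing visits after study discontinuation until none is missing, so early withdrawers with a baseline may already be meant. This reading is open, but the text does not settle it. Filling every visit can equally apply within the mITT set, and no other set is named. Two analysts could build different datasets.

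**The patient set is a matter for the SAP.** Usually it is, and the SAP may name another set. Here, however, the protocol states the rule itself, three times and without exception. Including baseline-only patients would depart from its letter.

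**Keeping the primary set has a merit.** If the sensitivity analysis uses the same patients as the MMRM, only the missing-data assumption changes. This stands, and it is the reason to show both versions.

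**The effect is negligible.** Largely so. About 0.1 point in one supportive analysis would rarely matter, and the protocol encourages patients to stay in the study after stopping treatment (5.8), which limits the affected group. This holds the point at minor.

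**A stronger reading.** A reader might infer that the rule contradicts the ITT definition in the same section. It does not. Section 12.2.4 openly declares mITT as a modification of ITT for change from baseline, and the wording about patients not followed to Week 104 also fits those with some post-baseline data, whom the rule keeps.

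**Conclusion.** The point holds as a minor improvement to one sensitivity analysis. As written, the mITT rule reaches the placebo-based imputation and leaves out patients who withdraw from the study in about the first 12 weeks. With 30% dropout spread evenly or at constant hazard, that is 3.5-4.0% of patients, and a true benefit looks 3.6-4.2% larger. The count rests on the assumed timing. The relative inflation follows from the count once baseline-only patients are taken to contribute no drug effect, as imputation from placebo data implies.

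A reader might also infer a biased primary result or a raised false-positive risk. Neither follows: the primary MMRM estimate is unaffected, and the shift is zero when the drug has no effect. Patients who stop treatment but keep attending visits have post-baseline scores and are not affected.

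**What to change.** Add to 12.2.4.1, and reflect in the synopsis, that the placebo-based multiple imputation includes all randomized patients with a baseline ADAS-Cog13, whether or not a post-baseline value exists, and that the baseline-plus-post-baseline requirement in 12.1.1 and 12.2.4 does not apply to it. Report the same imputation in the mITT set alongside, so that the effect of the missing-data assumption can be separated from the effect of the patient set.

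The cost is a sentence in each place and a little programming, with no added visits or tests. The downsides are a slightly less favourable sensitivity estimate when the drug works (about 0.1 point under the 30% assumption) and a patient set that differs slightly from that of the primary MMRM.
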